ILD is considered an important identified risk for tepotinib in patients with advanced NSCLC due to the possible severity and mortality that can be associated with these events. This condition is known to occur in association with treatment with other TKIs or other MET inhibitors in the NSCLC setting. In the MS200095-0022 (VISION) study, 1 fatal case of acute respiratory failure secondary to an ILD-like event has been reported that was considered related to tepotinib by the Investigator. The causal relationship between ILD and tepotinib is confounded by the presence of other factors, such as the underlying NSCLC disease, smoking, prior anticancer treatments, the heterogeneity of manifestations, or the partly unconfirmed ILD diagnosis in some reported cases. However, due to the severity and mortality that can be often associated with this type of events, mitigation measures include careful monitoring in case of symptoms, withdrawal of treatment when ILD is suspected, treatment discontinuation and appropriate treatment for the event (eg, with steroids) upon ILD diagnosis. In summary, considering the severe implications of the condition, the risk can be well managed by the prompt diagnosis and permanent discontinuation of tepotinib treatment. For further details refer to the tepotinib IB.

Edema (mainly peripheral edema), creatinine increased, hypoalbuminemia, amylase and lipase increased, aspartate aminotransferase (AST) and alanine aminotransferase (ALT) increased, diarrhea, and nausea and vomiting are the risks that are considered adverse reactions to tepotinib. More detailed safety information on classification of risks is provided in the tepotinib IB.

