	1	2	3	4	5	6	7	8	9	10	11	12
De-escalate from 500 mg to 250 mg in case the number of DLTs is \geq	1	1	2	2	2	3	3	3	4	4	4	5
Escalate back from 250 mg to 500 mg in case the number of DLTs is \leq	0	0	0	0	1	1	1	1	2	2	2	2

DLT: Dose limiting toxicity

At least 6 participants on a dose level are regarded as necessary to select a dose for the Phase II part of the study. In the safety run-in part of the study, DLTs are defined as any of the following toxicities and judged by the Investigator and/or the Sponsor to be not attributable to the disease or disease-related processes under investigation:

- Grade 4 neutropenia for more than 7 days
- Grade ≥ 3 febrile neutropenia
- Grade 4 thrombocytopenia or Grade 3 thrombocytopenia with non-traumatic bleeding
- Grade ≥ 3 nausea/vomiting and/or diarrhea that has not improved within 72 hours despite adequate and optimal treatment
- Any other Grade ≥ 3 non-hematological AE, except alopecia or Grade 3 nausea/vomiting and/or diarrhea that has improved within 72 hours with optimal treatment.

A DLT is also defined specifically in case of:

- Occurrence of Hy's law cases (defined as aminotransferases $> 3 \times$ upper limit of normal (ULN), total bilirubin $\geq 2 \times$ ULN, and alkaline phosphatase (ALP) $< 2 \times$ ULN, with no other reason to account for these abnormalities)
- Grade ≥ 3 lipase and/or amylase elevation with signs and symptoms suggestive of pancreatitis or if confirmation of pancreatitis, either based on clinical or radiological signs. An isolated lipase and/or amylase elevation of Grade ≥ 3 without clinical or radiological evidence of pancreatitis will not be defined as DLT
- Any QTcF increase associated with signs and symptoms of serious arrhythmia (Grade 4)
- Interstitial lung disease/pneumonitis

[figure not shown]
All participants enrolled in safety run-in who miss $> 25\%$ of the planned doses within Cycle 1 will be replaced if the dose reduction/interruption was not caused by any safety reasons/DLTs.

b. MAIN TREATMENT

The main treatment part overview is provided in

[Figure 3.](#)

Figure 3 Main Treatment

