6.8 Special Precautions

The study will be performed at a clinical research site with personnel trained in basic or immediate life support. Equipment and other agents (epinephrine and prednisolone equivalents, etc.) will be available at the site in case of allergic reactions. In case of localized radiation therapy this should be discussed with the Sponsor (or delegate) on a case-by-case basis.

6.9 Management of Specific Adverse Events, Adverse Events of Special Interest or Adverse Drug Reactions

Tepotinib

Specific Adverse Events

Interstitial Lung Disease

Interstitial lung disease or ILD-like adverse reactions have been reported in the clinical study program with tepotinib in patients with NSCLC.

Participants should be monitored for pulmonary symptoms indicative for ILD or ILD-like reactions. Tepotinib should be withheld and participants should be promptly investigated for alternative diagnosis or specific etiology of ILD. Tepotinib must be permanently discontinued if ILD is confirmed and the participant be treated appropriately.

Edema

Edema has been reported frequently in the study program. It is an identified risk for treatment with tepotinib. Other AEs related to fluid retention, such as generalized edema and pleural effusion have been observed. To gain further information to the occurrence and resolution of edema, any AEs of edema, the current edema status or AE resolution is to be specifically documented at each visit.

In the case of edema, please follow the advice provided in Table 3 in Section [6.6](#).

Asymptomatic Pancreatic Enzyme Elevation

If an asymptomatic lipase/amylase elevation of Grade ≥ 3 occurs, the participant will undergo clinical evaluation for the presence of signs and symptoms typical of acute pancreatitis and for

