TEAEs are those events that started during the on-treatment periods (see Section 9.3), or before Period 1 and worsened during the on-treatment periods. This includes also AEs ongoing at baseline, which first improve under study treatment and then worsen irrespective of baseline. The rules defined in Table 10 will be used to assign TEAEs to the on-treatment periods. Any AE occurring before Period 1 and resolved before Period 1 or not worsening during the on-treatment periods will be included in the AE listings, but will not be included in the TEAE summary tables (unless otherwise stated). Adverse events with changes in toxicity grade are recorded as separate entries in the eCRF with associated end and start dates (start date equals end date of previous entry, supported in eCRF by 'AENEWID' in SUPPAE). Records of the same AE will be considered as one event in the analysis. These events will be kept as separate records in the database in order to maintain the full detailed history of the events. In AE listings, records that are part of the same AE will be grouped together and presented in chronological order. If the severity of the reported event worsens after start of treatment, the TEAE flag will be re-evaluated for the worse and the subsequent records as per the TEAE definition: once one record is considered treatment emergent, all the subsequent records will be considered treatment emergent too, even if starting after the ontreatment periods.

All analyses described in Sections 15.2.2 and 15.2.3 will be based on TEAEs belonging to Period 1, if not otherwise specified. The AE listings will include all AEs (whether treatment emergent or not). A flag will be added to indicate if the AE is treatment emergent and in which period.

Unless otherwise specified, TEAEs will be summarized by number and percentage of participants with the TEAE in the category of interest and sorted by primary SOC and PT in alphabetic order.

Each participant will be counted only once within each SOC or PT. If a participant experiences more than one AE within an SOC or PT for the same summary period, only the AE with the strongest relationship or the worst severity, as appropriate, will be included in the summaries of relationship and severity.

Table 10.	Assignment of TEAEs to the on-treatment periods

	TEAE in Period 1	TEAE in Period 2
Starts before Period 1 and worsens during Period 1	Х	
Starts before Period 1 and worsens during Period 2		Х

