Starts in Period 1 (regardless of worsening in Period 2)	Х	
Starts in Period 2		Х

15.2.2All Adverse Events

Adverse Event information is collected on the "Adverse Events Details" eCRF page.

Adverse events will be summarized by worst severity (according to NCI-CTCAE version 5.0) per participant, using the latest version of MedDRA PT as event category and MedDRA primary SOC body term as Body System category.

In case a participant has events with missing and non-missing grades, the maximum of the nonmissing grades will be displayed. No imputation of missing grades will be performed.

The overall summary of AEs table will include the frequency (number and percentage) of participants with each of the following:

- TEAEs
- Study treatment related TEAEs (any study treatment and by study treatment components)
- Serious TEAEs
- Study treatment related serious TEAEs (any study treatment and by study treatment components)
- TEAEs with NCI-CTCAE Grade \geq 3 and \geq 4
- Study treatment related TEAEs with NCI-CTCAE Grade ≥ 3 and ≥ 4 (any study treatment and by study treatment components)
- TEAEs leading to death
- Study treatment related TEAEs leading to death (any study treatment and by study treatment components)
- Adverse Events of Special Interest (AESIs)

Adverse events of special interest are defined as events suggestive of drug-induced liver injury including hepatic / liver failure and hepatitis (non-infectious). Adverse Events of Special Interest (AESI) will be identified according to a pre-specified search list provided by the Sponsor Safety Lead using the last available version of MedDRA Preferred Terms at the time of each analysis.

In addition, the following tables summarizing the frequency of participants with TEAEs by SOC and PT will be produced:

- TEAEs
- Study treatment related TEAEs (any study treatment and by study treatment components)
- Serious TEAEs
- Non-serious TEAEs applying a frequency threshold of 5%
- Study treatment related serious TEAEs (any study treatment and by study treatment components)
- TEAEs by worst NCI-CTCAE Grade (Any, ≥ 3 , ≥ 4 and 5)
- Study treatment related TEAEs by worst NCI-CTCAE Grade (Any, ≥ 3 , ≥ 4 and 5) (any study treatment and by study treatment components)

- TEAEs leading to death
- Study treatment related TEAEs leading to death (any study treatment and by study treatment components)
- Adverse Events of Special Interest (AESIs)

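### The SAP pre-specifies no grouped count for edema or for ILD/pneumonitis and no summary of edema onset or resolution, so participant-level figures for these two identified risks cannot be read from the planned tables

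*SAP*

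**What the plan says.** **Protocol.** Section 6.9 says of edema: "It is an identified risk for treatment with tepotinib". To learn about its occurrence and resolution, sites are told that "any AEs of edema, the current edema status or AE resolution is to be specifically documented at each visit". The same paragraph adds: "Other AEs related to fluid retention, such as generalized edema and pleural effusion have been observed". Section 2.3 states that "ILD is considered an important identified risk for tepotinib in patients with advanced NSCLC" and describes a fatal case of respiratory failure secondary to an ILD-like event. Section 4.1 includes "Interstitial lung disease/pneumonitis" among the dose-limiting toxicities of the safety run-in.

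**SAP.** Section 15.2.2 sets up one term group for a tepotinib risk: "Adverse events of special interest are defined as events suggestive of drug-induced liver injury". That group is identified from a sponsor search list of MedDRA preferred terms. Everything else is presented by system organ class (SOC) and PT: "In addition, the following tables summarizing the frequency of participants with TEAEs by SOC and PT will be produced". The counting rule in 15.2.1 is "Each participant will be counted only once within each SOC or PT". Section 15.3.3, on other significant adverse events, only points back to the AESI analysis. The words edema, fluid retention, ILD and pneumonitis do not occur in the SAP.

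**The concern.** The protocol asks a specific safety question about edema: how often it occurs and whether it resolves. It also singles out ILD for its severity. The analysis plan has no output that answers either at the level of the participant.

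A reader of the study report would want the number of participants with any edema, their worst grade, when it began and whether it cleared, and the number with any ILD or pneumonitis. If an event type is coded to several PTs, these figures are spread over rows that cannot be summed. Someone quoting the largest row would then be quoting a lower bound.

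A grouped count added later would be an unplanned analysis, which SAP Section 4 requires the study report to identify as such. The study is open-label, and SAP 6.2 gives the sponsor the IDMC outputs from the second meeting onwards, so the terms would be chosen with knowledge of the data.

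**Working it through.** No sample size, power or rate in the documents bears on this point, so there is no stated figure to reproduce. The check has two parts.

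**1. What the planned tables show for an edema or ILD event**

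| Question | Planned output | Readable per participant, across terms? |
|---|---|---|
| Incidence | SOC/PT tables of all, related (by component), serious and fatal TEAEs (SAP 15.2.2) | No, per PT only |
| Worst grade | SOC/PT tables, any, ≥3, ≥4 and 5 (15.2.2) | No, per PT only |
| Interruption, discontinuation, dose reduction | SOC/PT tables, by component (15.2.3) | No, per PT only |
| Run-in DLTs | Table with SOC and PT (15.1) | Run-in participants only |
| Onset, duration, resolution | AE listings; grade changes shown in date order (15.2.1, 15.2.2) | Listing only, no summary |
| Edema status recorded at visits | None named | No |

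The SOC row does not help, because it also counts unrelated events in the same organ class.

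**2. Size of the possible gap**

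Let p₁, …, p_k be the PT rates within one medical concept. The proportion G with at least one of them satisfies

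max(pᵢ) ≤ G ≤ min(1, Σpᵢ),

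and if the terms occurred independently, G = 1 − Π(1 − pᵢ). The lower bound is complete overlap; the upper bound is no overlap. The documents give no edema or ILD PT rates for tepotinib, so every rate below is an assumption.

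| Assumed PT rates | Largest row | Independent | No overlap |
|---|---|---|---|
| 20%, 10%, 10% | 20% | 1 − 0.80×0.90×0.90 = 35.2% | 40% |
| 20%, 10%, 5% | 20% | 1 − 0.80×0.90×0.95 = 31.6% | 35% |
| 40%, 5%, 5% | 40% | 1 − 0.60×0.95×0.95 = 45.9% | 50% |
| 4%, 2%, 1% (ILD) | 4% | 1 − 0.96×0.98×0.99 = 6.9% | 7% |

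The largest row therefore falls short of the grouped rate by anything from zero to the sum of the smaller PT rates. Protocol 2.3 describes the edema risk as mainly peripheral. That implies more than one kind of edema, but also that one term may dominate, in which case the gap is small.

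**The case against.** The strongest reply is that these events are analysed. Every edema and ILD TEAE appears by PT, grade, relationship, seriousness and action taken, each PT count is correct, and dates are in the listings. ILD also counts as a run-in DLT. This stands. A reader might infer that the SAP leaves edema and ILD out altogether, or that their rates will be understated. The documents support neither: what is missing is a grouped count and an edema summary, and the shortfall may be zero.

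Second, the SAP follows the protocol, which limits AESIs to liver injury in 6.9, 9.4.2 and Appendix 4 and plans no other grouping. True; no protocol-planned analysis was dropped. The request is for an analysis grouping and leaves the AESI definition and expedited reporting alone.

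Third, a separate edema dataset may not exist. The Schedule of Activities has no edema row and the SAP cites no edema eCRF page, so the visit documentation may be no more than the AE record. This also stands, and the edema summary should rest on AE start and end dates.

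Fourth, pooling pleural effusion with edema could overstate fluid retention. Protocol 8.1 calls for cytology of punctured effusions to look for malignancy, so some may be tumor-related. Accepted.

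Finally, a reader might take edema and ILD to be tepotinib's main harms or the chief causes of interruption. The documents do not show this. Protocol 2.3 lists other reactions, several covered by the laboratory analyses, and no interruption frequencies by cause are given for tepotinib.

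The output tracker named in SAP Appendix 4 was not available. It is described as a list of outputs; the SAP text itself holds no term list or derivation for either group.

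**Conclusion.** The point holds as a gap in pre-specification. From the planned tables one cannot read how many participants had any edema or any ILD/pneumonitis, nor the worst grade or action taken at that level, and no summary of edema onset or resolution is planned.

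The consequence is possible rather than certain understatement, bounded by zero and the sum of the smaller PT rates. With assumed rates of 20%, 10% and 10%, that is 0 to 20 percentage points. It rests on two assumptions the documents do not settle: that each event type is coded to more than one PT, and that overlap between those PTs is incomplete. The efficacy analyses are unaffected. This is a cheap improvement that lets the trial answer a safety question its own protocol poses.

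**What to change.** In SAP 15.2.2 and 15.3.3:

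- Pre-specify PT lists for (a) edema and (b) ILD/pneumonitis through the sponsor search-list process already used for AESIs, fixed before database lock. Leave the AESI definition unchanged.
- For each group, by arm and for Period 1, report participants with any event, by worst grade, with a serious event, and with an event leading to interruption, dose reduction or permanent discontinuation.
- For edema, add descriptive time to first onset, number resolved, and duration from AE start and end dates, using the date conventions of SAP 9.5 and 9.9. List any edema status recorded at visits.
- Show pleural effusion as a separate row or as a sensitivity grouping.
- For ILD, list onset and outcome case by case. With about 12 centrally confirmed monotherapy participants and probably few events, Kaplan-Meier onset curves would add little to the listing.

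The cost is two PT lists, a few tables and a judgement on which PTs to include. The AE summaries need no new data collection, and no clinical rule changes.

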9.4.2 Safety Analyses

All safety analyses will be performed on the SAF. All analyses will be presented by treatment arm and by dose level, if applicable, and participants will be analyzed as treated.

The safety analyses will also be done purely descriptively.

Endpoint	Statistical Analysis Methods
Primary (for the safety run-in)	
Occurrence of DLTs	Refer to Section 4.1 for the definition of DLTs The number and percentage of participants in the DLT analysis set during the DLT observation period will be tabulated.
Secondary	
Occurrence of AEs and treatment-related AEs and deaths during the study	
Adverse events will be coded according to the latest available version of the Medical Dictionary for Regulatory Activities. Severity of AEs will be graded using the NCI-CTCAE (v5.0) toxicity grades. AEs related to study intervention will be defined as any AE considered as related to tepotinib and/or osimertinib. Missing classifications concerning study intervention relationships will be considered related to the study intervention.
 
Any TEAEs will be summarized, ie, those events that are emergent during treatment having been absent prior to treatment or worsened relative to the pretreatment state and with onset dates occurring within the first dosing day of study intervention until 30 days after the last dose of study intervention (or switch over to combination treatment, whichever occurs first for the tepotinib monotherapy arm). Adverse events occurring after switch over will be described separately, details will be specified in the IAP.
 
Following subtypes of TEAEs will be presented in summaries and tables according to System Organ Classes and Preferred Terms:
 
 • TEAEs • SAEs • TEAEs related to tepotinib and/or osimertinib • SAEs related to tepotinib and/or osimertinib • NCI-CTCAE Grade 3 or higher TEAEs • NCI-CTCAE Grade 3 or higher TEAEs related to tepotinib and/or osimertinib • TEAEs leading to tepotinib and/or osimertinib interruptions • TEAEs leading to permanent tepotinib and/or osimertinib discontinuation • TEAEs leading to deaths. • AESIs 
Deaths during the study will also be presented in summaries and tables.
 
Adverse events of special interest are defined as events suggestive of drug-induced liver injury including hepatic/liver failure and hepatitis (non-infectious) and are

Endpoint	Statistical Analysis Methods

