9.3 Definition of On-treatment Periods

Participants in the monotherapy arm will be allowed to switch to the combination treatment once PD is confirmed. The following on-treatment periods are defined in order to indicate which data will be used for the analyses.

Table 3.	On-treatment Periods
----------	-----------------------------

		Combination Arm	Monotherapy Arm - No Switch	Monotherapy Arm – Switch ^a
Period 1	Start	First dose of study treatment	First dose of study treatment	First dose of study treatment
	End	Last dose of study treatment + 30 days or the cut-off date or death, whichever occurs first	Last dose of study treatment + 30 days or the cut-off date or death, whichever occurs first	First dose of osimertinib ^b
Period 2	Start	NA	NA	First dose of osimertinib ^b
	End	NA	NA	Last dose of combination treatment ^c + 30 days or the cut-off date or death, whichever occurs first

a: Unless stated otherwise, data from Period 1 will contribute to tables, figures and listings whereas data from Period 2 to study discontinuation will only be listed.

b: Measurements collected on the day of the start of the combination treatment will be considered to belong to Period 1 unless clearly collected after the first administration of osimertinib. The same rule applies to adverse events.

c: The last dose of the combination treatment is considered as the last dose of tepotinib or osimertinib, whichever is later.

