Participant listings of AE details collected on the "Adverse Events Details" eCRF page will also be provided:

- AEs
- AESIs
- Serious TEAEs

The overall AE summary table as well as the TEAEs by SOC and PT table will be repeated if there are at least 6 participants in the monotherapy arm who switch to the combination treatment. For these tables, all TEAEs from both Period 1 and Period 2 (see Table 10) will be considered. Results will be presented overall, i.e. there will be no split by MET amplification test result.

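### SAP 15.2.2 combines adverse events from before and after the switch, so no AE table gives the separate post-switch description that Protocol 9.4.2 announces

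*SAP*

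**What the plan says.** **Protocol 9.4.2.** For the monotherapy arm the TEAE window ends 30 days after the last dose "or switch over to combination treatment, whichever occurs first for the tepotinib monotherapy arm". The next sentence deals with what follows: "Adverse events occurring after switch over will be described separately, details will be specified in the IAP".

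**SAP 9.3, Table 3.** For switchers, Period 2 begins at the first osimertinib dose. Footnote a sets the default that "data from Period 2 to study discontinuation will only be listed".

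**SAP 15.2.1.** "All analyses described in Sections 15.2.2 and 15.2.3 will be based on TEAEs belonging to Period 1, if not otherwise specified". Each participant counts once per SOC or PT. AE listings carry a flag for the period in which an event was treatment-emergent. Table 10 places an event that starts in Period 1 in Period 1, whether or not it worsens in Period 2.

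**SAP 15.2.2.** This section holds the one exception among the AE tables. The overall AE summary and the TEAE table by SOC and PT "will be repeated if there are at least 6 participants in the monotherapy arm who switch to the combination treatment". Their content is then defined: "For these tables, all TEAEs from both Period 1 and Period 2 (see Table 10) will be considered". They are shown overall, which the SAP explains as not splitting by MET test result. No column by period and no denominator is given.

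**SAP 15.3.1.** Deaths from both periods are tabulated without a stated split. Period 2 deaths are flagged in the listing.

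**The concern.** The protocol separates events after the switch from events before it and hands the detail to the SAP. The SAP's rule for its repeated tables joins the two. A participant in Period 1 takes tepotinib alone; in Period 2 osimertinib has been added. A count over both periods describes neither exposure.

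The post-switch exposure is one a safety reader will ask about. Protocol 2.3 names interstitial lung disease as an important identified risk of tepotinib, and reports it in 4% and QTc prolongation in 10% of osimertinib-treated participants in the first-line trial it cites. Followed as written, the SAP yields no table with the number of switchers who had a given event after osimertinib was added.

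Table 10 adds a second gap. An event that begins on tepotinib alone and becomes more severe after the switch is never attributed to Period 2. An event that began before any study treatment and worsens in Period 2 is attributed to Period 2, so the two kinds of worsening are handled differently.

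**Working it through.** The plan states no figure on this point, so there is none to reproduce. The check is a comparison of texts followed by two short calculations.

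**1. Which AE tables contain post-switch events?**

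| Output | Period covered | Post-switch counts readable? |
|---|---|---|
| Tables of SAP 15.2.2 and 15.2.3 (default) | Period 1 | No |
| Repeated overall summary and SOC/PT table (15.2.2) | Periods 1 and 2 together, if 6 or more switch | Not separately |
| AE listings (15.2.1) | All, with period flag | Per participant only |
| Deaths table (15.3.1) | Both, no stated split | Only through the flagged listing |

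**2. Can the post-switch count be found by comparing the repeated table with the Period 1 table?** For one term and the same participants, let A be the proportion with it in Period 1, B in Period 2, O in both, and C in the combined table. Because each participant counts once, C = A + B − O, so B = C − A + O. O is not reported and can run from 0 to A, so B lies between C − A and C. If the periods were independent, B = 1 − (1 − C)/(1 − A). The proportions below are illustrative.

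| A shown | C shown | B, no overlap (C − A) | B, full overlap (C) | B, if independent |
|---|---|---|---|---|
| 10% | 37% | 27% | 37% | 1 − 0.63/0.90 = 30% |
| 30% | 37% | 7% | 37% | 1 − 0.63/0.70 = 10% |
| 20% | 36% | 16% | 36% | 1 − 0.64/0.80 = 20% |

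In the first row a rise is visible despite the uncertainty. In the second, a fall to 7% and a rise to 37% fit the same two tables.

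The bounds also need a common denominator, which the SAP does not give. If the repeated table is over all 12 monotherapy participants and 6 switched, one added participant reads as 1/12 = 8.3%, but is 1/6 = 16.7% of those exposed.

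**3. How often would there be no repeated table?** The inputs are the threshold of 6 (SAP 15.2.2) and the planned 12 monotherapy participants (Protocol 9.2). The switch proportion p is not in the documents and is assumed. N can exceed 12, because randomization runs until 12 centrally confirmed participants are in the arm and locally positive, unconfirmed ones add to it; N = 16 illustrates this. The probability is P(X ≤ 5), with X binomial (N, p).

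| p | 0.3 | 0.4 | 0.5 | 0.6 | 0.7 | 0.8 |
|---|---|---|---|---|---|---|
| N = 12 | 0.88 | 0.67 | 0.39 | 0.16 | 0.04 | 0.004 |
| N = 16 | 0.66 | 0.33 | 0.11 | 0.02 | 0.002 | <0.001 |

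The threshold matters if about half or fewer switch and hardly at all if 70% or more do. The combining of periods does not depend on the number.

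**The case against.** The protocol promises a description, not a table. The SAP keeps Period 2 events out of the main tables, lists all AEs with their period, and flags Period 2 deaths. SAP 7 declares openly that rules for switchers were added. This stands in part: every post-switch event can be identified. A reader might infer that post-switch safety cannot be seen anywhere, and the documents do not support that. What is missing is a count or percentage. SAP 7 does not say that the separate description is given up, and the SAP itself judged a table worthwhile when enough participants switch.

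The Period 1 tables are still produced. A reader might infer that 10% before and 30% after cannot be told from 30% before and 10% after, since both combine to 37% under independence. That is too strong: the Period 1 table shows 10% in one case and 30% in the other. What remains is the narrower point that the size, and sometimes the direction, of the change depends on the unreported overlap and the unstated denominator.

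The SAP does not literally forbid period columns. It refers to Table 10, and output details sit in a tracker outside these documents. Combining is the natural reading, not the only possible one.

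The 6-participant condition resembles the SAP's small-number rule for laboratory and ECG visits (15.4 and 15.6.2). With 5 or fewer switchers a flagged listing shows everything. Removing the condition is largely a preference.

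Period 2 laboratory, ECG and vital-sign data are only listed. A reader might take that as a further breach, but the protocol sentence concerns adverse events only.

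**Conclusion.** The point holds for AE tables. The SAP's rule for its repeated tables does not deliver the separate post-switch description in Protocol 9.4.2: periods are combined, the denominator is unstated, and events that start in Period 1 and worsen after the switch never count in Period 2. This rests on reading SAP 15.2.2 as combining the periods, since no split is specified.

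The consequence is limited. It touches neither the primary endpoint nor the main safety comparison by arm, safety is descriptive throughout, and most information on the combination will come from the combination arm, where 80 participants are planned in the primary analysis set. It should still be corrected, because the post-switch counts cannot be reliably recovered from the planned tables: in the 30%/37% example they range from 7% to 37%. How likely the tables are to be omitted altogether depends on a switch rate that the documents do not give.

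**What to change.** In SAP 15.2.2:

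- Present the repeated overall AE summary and SOC/PT table for Period 2 only, or add a separate Period 2 column. Use participants who switched as the denominator and the first osimertinib dose as the start.
- For these tables, state an exception to Table 10: an event that starts in Period 1 and worsens in Period 2 also counts in Period 2, at its worst Period 2 grade. Without it, a Period 2 table would miss worsening after the switch.
- Keep the version covering both periods, if wanted, as a supplement with its denominator stated.
- If fewer than 6 switch, either show the counts or say that a separate Period 2 AE listing serves as the description the protocol announces.

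The cost is SAP wording, a filter on period flags already derived, and one added derivation rule for worsening. No new data and no change in study conduct are needed. Cells will be small, so the counts are descriptive only.
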